7.2.3 Dose Modification

There will be no dose adjustments in this study.

7.2.4 Dose Interruptions

If a subject experiences an AE that requires interruption in study drug, the investigator should consult with the Sponsor medical monitor to evaluate the need for any additional tests prior to re-starting study drug.

7.3 Blinding and Unblinding

Blinding is critical to the integrity of this clinical study. However, in the event of a medical emergency or pregnancy in an individual subject, in which knowledge of the investigational product is critical to the subject's management, the blind for that subject may be broken by the treating physician.

Before breaking the blind of an individual subject's treatment, the investigator should have determined that the information is necessary, (i.e., that it will alter the subject's immediate management). In many cases, particularly when the emergency is clearly not investigational product related, the problem may be properly managed by assuming that the subject is receiving active product without the need for unblinding.

In cases of accidental unblinding, contact the Medical Monitor and ensure every attempt to preserve the blind is made.

7.4 Treatment Compliance

Responsible study personnel will dispense the study drug. Subjects are required to finish a wallet of study drug before starting a new wallet. Accountability and compliance verification should be documented in the subject's study records.

Subjects must be counseled on the importance of taking the study drug as directed (see Section 7.2.2). Treatment compliance and review of study drug doses through review of returned study drug should be assessed by site staff at each study visit. Discrepancies between review of study drug and information provided by subject must be documented in the source record. Investigators should inform subjects that involuntary termination from the study will occur in cases where non-compliance is identified. Study staff should contact a subject between the monthly study visits if the subject demonstrates non-compliance with the eDiary and document the contact in the source, to identify potential lost to follow-up subjects as early as possible.

Investigators must monitor subjects for possible cases of abuse of study drug (subjects taking study drug for non-therapeutic purposes, e.g. for psychoactive effects such as high or euphoria). Investigators should also assess study drug accountability discrepancies (e.g. missing study drug, loss of medication, or non-compliance cases in which more study drug was used, as compared to expected). Investigators should obtain more information and explanation from subjects when there are study drug accountability discrepancies. (See Section 8.1.1.)

Cases of potential study drug abuse or overdose (including cases of non-compliance with study drug dosing instructions or subjects who discontinue treatment without returning study drug) should be documented in the source record and reported as an AE or SAE as appropriate. Dosing errors (e.g. accidentally taking 2 tablets in one calendar day) should be reported as deviations.

Compliance with study intervention will be defined as:

- ≥80% (and ideally, up to 100%) of study-supplied intervention from Day 1 through the Treatment Phase are expected to be consumed.
- Post randomization, at each dispensation visit (refer to Table 1), subjects who are <80% compliant must be re-educated on the importance of daily selfadministration of study intervention.
- Overall aim: maintain ≥80% compliance over the duration of dosing with randomized study intervention.

7.5 Destruction and Return of Study Drug

All unused and/or partially used study drug can be sent to the predetermined drug destruction facility only after being inspected and reconciled by the responsible Study monitor or the sponsor's designee. If it is site policy to destroy study drug on site, it is the Investigator's responsibility to ensure that arrangements have been made for the disposal, procedures for proper disposal have been established according to the applicable regulations, guidelines and institutional procedures, and appropriate records of the disposal have been documented. Destruction at a study site may only occur after being inspected and reconciled by the responsible Study monitor or the sponsor's designee.

8 ADVERSE EVENTS

An Adverse Event (AE) is defined as any new untoward medical occurrence or worsening of a pre-existing medical condition in a subject or clinical investigation subject administered an investigational (medicinal) product and that does not necessarily have a causal relationship with this treatment. An AE can therefore be any unfavorable and unintended sign (including an abnormal laboratory finding for example) symptom, or disease temporally associated with the use of the investigational product, whether or not considered related to the investigational product.

Adverse events can be spontaneously reported or elicited during an open-ended questioning, examination, or evaluation of a subject. In order to prevent reporting bias, subjects should not be questioned regarding the specific occurrence of one or more AEs.

If a specific diagnosis or syndrome is identified by the Investigator, this should be recorded as the AE, rather than recording (as separate AEs) the individual signs/symptoms or clinically significant laboratory abnormalities known to be associated with and considered by the Investigator to be a component of, the disease/syndrome.

Definition of terms related to all AEs (serious and non-serious):

Mild: Is usually transient and may require only minimal treatment or therapeutic intervention. The event does not generally interfere with usual activities of daily living.

Moderate: Is usually alleviated with additional specific therapeutic intervention. The event interferes with usual activities of daily living, causing discomfort but poses no significant or permanent risk of harm to the subject.

Severe: Interrupts usual activities of daily living, significantly affects clinical status, or may require intensive therapeutic intervention.

Life threatening: An AE is life threatening if the subject was at immediate risk of death from the event as it occurred, i.e., it does not include a reaction that if it had occurred in a more serious form might have caused death. For example, drug induced hepatitis that resolved without

evidence of hepatic failure would not be considered life threatening even though drug induced hepatitis can be fatal.

Hospitalization: AEs requiring hospitalization should be considered SAEs. Hospitalization for elective surgery or routine clinical procedures that are not the result of AE (e.g., elective surgery for a pre-existing condition that has not worsened) need not be considered AEs or SAEs. If anything untoward is reported during the procedure, that occurrence must be reported as an AE, either 'serious' or 'non-serious' according to the usual criteria.

Assessment for Determining Relationship of AE to Study Drug:

The relatedness of each AE to study drug must be classified based on medical judgement and according to the following categories. The definitions are as follows:

Related: This category applies to AEs that are considered, with a high degree of certainty, to be related to the study drug. An AE may be considered related when it follows a temporal sequence from the administration of study drug, it cannot reasonably be explained by the known characteristics of the subject's clinical state, environment, or toxic factors, or other modes of therapy administered to the subject. An AE may be considered related when it follows a known pattern of response to the study drug, or if the AE reappears upon re-challenge.

Possibly related (non-serious AEs only): This category applies to AEs that are considered to have an unlikely connection to study drug, but a relationship cannot be ruled out with certainty.

Unlikely related (non-serious AEs only): This category applies to AEs that do not follow a reasonable temporal sequence from the administration of the study drug. The AE may readily have been produced by the subject's clinical state, environmental or toxic factors, or other modes of therapy administered to the subject.

Unrelated: This category applies to AEs that are considered with a high degree of certainty to be due only to extraneous causes (e.g. subject's clinical state, environment, toxic factors, disease under study, etc.) and does not meet the criteria of other categories above.

There are two types of adverse events, Serious Adverse Events (SAE) and Non-serious Adverse Events (AEs).

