If EDP occurs in a subject/subject's partner, the investigator must report this information to Pfizer Safety using the CT SAE Report Form or via PSSA, regardless of whether an SAE has occurred. Details of the pregnancy will be collected after the start of study intervention and until 66 hours after the last dose.

If EDP occurs in the setting of environmental exposure, the investigator must report information to Pfizer Safety using the CT SAE Report Form or via PSSA. Since the exposure information does not pertain to the subject enrolled in the study, the information is not recorded on a CRF; however, a copy of the completed report is maintained in the investigator site file. Follow-up is conducted to obtain general information on the pregnancy and its outcome for all EDP reports with an unknown outcome. The investigator will follow the pregnancy until completion (or until pregnancy termination) and notify Pfizer Safety of the outcome as a follow-up to the initial report. In the case of a live birth, the structural integrity of the neonate

can be assessed at the time of birth. In the event of a termination, the reason(s) for termination should be specified and, if clinically possible, the structural integrity of the terminated fetus should be assessed by gross visual inspection (unless pre-procedure test findings are conclusive for a congenital anomaly and the findings are reported).

Abnormal pregnancy outcomes are considered SAEs. If the outcome of the pregnancy meets the criteria for an SAE (ie, ectopic pregnancy, spontaneous abortion, intrauterine fetal demise, neonatal death, or congenital anomaly in a live-born baby, a terminated fetus, an intrauterine fetal demise, or a neonatal death), the investigator should follow the procedures for reporting SAEs. Additional information about pregnancy outcomes that are reported to Pfizer Safety as SAEs follows:

- Spontaneous abortion including miscarriage and missed abortion should be reported as an SAE;
- Neonatal deaths that occur within 1 month of birth should be reported, without regard to causality, as SAEs. In addition, infant deaths after 1 month should be reported as SAEs when the investigator assesses the infant death as related or possibly related to exposure to the study intervention.

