10 ETHICS AND RESPONSIBILITIES

10.1 Good Clinical Practice

This study will be conducted in compliance with the protocol, Good Clinical Practice (GCP), Good Laboratory Practice (GLP), International Conference on Harmonization guidelines, and all applicable regulations, including the Federal Food, Drug and Cosmetic Act, U.S. applicable Code of Federal Regulations (title 21), any Independent Ethics Committee (IEC) requirements relative to clinical studies. The study will also be conducted in compliance with the recommendations laid down in the most recent version of the Declaration of Helsinki. This study will be conducted in compliance with the protocol. The protocol and any amendments and the subject informed consent will receive Institutional Review Board/Independent Ethics Committee (IRB/IEC) approval/favorable opinion prior to initiation of the study.

The Sponsor is responsible for ensuring that all updated relevant information related to the protocol be submitted to regulatory authorities and Independent Ethics Committees in accordance with local laws and regulations. This includes expedited reporting of suspected unexpected serious adverse reactions per regulatory guidelines.

All serious breaches must be reported to Pfizer (or designee) immediately. A Serious breach is a breach of the conditions and principles of GCP in connection with the study or protocol, which is likely to affect, to a significant degree, the safety or physical or mental integrity of the subjects of the study or the scientific value of the study.

Study personnel involved in conducting this study will be qualified by education, training, and experience to perform their respective task(s).

This study will not use the services of study personnel where sanctions have been invoked or where there has been scientific misconduct or fraud (e.g., loss of medical licensure, debarment).

It is the Sponsor's responsibility to submit the protocol and its amendments (if any), and the ICFs to regulatory authorities when necessary.

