6.4.1.2 AE Overviews

An AE overview frequency table displays the following categories without SOC and PT: any AE; AE related to study drug; AE leading to study drug discontinuation; SAE; SAE related to study drug; medication-overuse headache AE; hepatic-related AE; hepatic-related AE leading to study drug discontinuation; potential drug abuse AE; cardiovascular AE; suicidality AE; hypertension AE; and Raynaud's phenomenon AE.

AE overview frequency tables are provided for the following safety analysis periods and analysis sets:

- On-DBT for the DBT safety analysis set
- Post-DBT pre-OL rimegepant for the interim safety analysis set
- On-OL rimegepant for the OL rimegepant safety analysis set
- On-DB or OL rimegepant for the DB or OL rimegepant safety analysis set
- Follow-up for the follow-up safety analysis set.

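### The causality scale leaves serious adverse events only two categories, both requiring high certainty, so a serious event of uncertain cause fits neither

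*Protocol*

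**What the plan says.** Protocol Section 8 makes the classification compulsory for serious and non-serious events alike: "The relatedness of each AE to study drug must be classified based on medical judgement and according to the following categories". Four categories follow.

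- *Related*: "This category applies to AEs that are considered, with a high degree of certainty, to be related to the study drug". Supporting sentences say when an AE may be placed here: the timing fits and nothing else reasonably explains it, it matches a recognised response to the drug, or it returns on re-exposure.
- *Possibly related*, labelled "Possibly related (non-serious AEs only" and defined as an event "considered to have an unlikely connection to study drug, but a relationship cannot be ruled out with certainty".
- *Unlikely related*, also limited to non-serious AEs and defined by the absence of a reasonable time relationship.
- *Unrelated*: "This category applies to AEs that are considered with a high degree of certainty to be due only to extraneous causes". The event must also fail the criteria of the other categories.

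Protocol 8.5.1 asks for infant deaths after the first month to be reported as SAEs "when the investigator assesses the infant death as related or possibly related to exposure to the study intervention". Protocol 9.3.2 plans a four-level tabulation of AEs by relationship. SAP 6.4.1.2 includes the overview rows "SAE; SAE related to study drug", and SAP 6.4.1.3 and 6.4.1.4 add tables of related AEs by worst intensity. SAP 6.4.1 refers to the Core SAP for what counts as related.

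**The concern.** A two-level causality scale for SAEs is workable if the two levels meet. Here they do not. Each is defined by strong certainty, one at each end, and nothing covers the ground between. Many serious events cannot be attributed with confidence when first reported, because the timing fits but the patient also has another illness or takes another drug. The investigator must still record a category. With no rule for such cases, two sites could classify the same event in opposite ways, and neither would be following the text.

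At stake are the meaning of the recorded SAE causality and of every output built on it.

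**Working it through.** No arithmetic applies. The check takes one test case through the definitions and then compares the other sections that rely on them.

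**Test case.** An SAE starts at a plausible time after dosing. A concurrent illness could also explain it. It matches no recognised response to the drug, and the drug has not been given again.

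| Category | Open to SAEs? | Does the test case meet it? |
|---|---|---|
| *Related* | Yes | No: high certainty is lacking |
| *Possibly related* | No | Closed |
| *Unlikely related* | No | Closed; the timing is also plausible |
| *Unrelated* | Yes | No: outside causes are not the only candidates |

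Of four categories, two are open to SAEs. Both need high certainty, and the test case meets neither.

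**Do the supporting sentences under *Related* close the gap?** Only in part.

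- The first route fails because the concurrent illness is a reasonable alternative explanation.
- The second needs a known response pattern, which a previously unrecognised reaction would not have.
- The third needs re-exposure.

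An SAE with no competing cause, or one that fits a known pattern, can reach *Related* this way. The gap therefore concerns mainly SAEs with a credible alternative cause.

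**Is *Unrelated* a natural default?** Not on its wording. It demands certainty of extraneous causes only, and a possible drug cause defeats that. If the other categories' criteria are read by content, the event also matches *Possibly related*, because a relationship cannot be excluded. The second condition of *Unrelated* then fails as well.

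**Comparison with other sections.**

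- Protocol 8.5.1 uses a possibly-related grade to decide SAE reporting of later infant deaths, although Section 8 closes that grade to SAEs.
- Protocol 8.2.1 has a non-serious AE reported as an SAE if it becomes serious. An event graded *Possibly related* then loses its category, and nothing says where it goes.
- Protocol 8.1.2 requires causality among the SAE details entered by the site. It collects all SAEs through Follow-up Week 8 and requires reporting within 24 hours, whether related or not. After that visit, it asks for SAEs believed to be related to study drug or protocol procedures.
- Protocol 9.3.2 lists the four levels without noting that two are unavailable for SAEs.
- SAP 6.4.1.2 carries the related-SAE row in overview tables for five combinations of safety period and analysis set.

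**The non-serious scale.** *Possibly related* is described as an unlikely connection, which blurs it with *Unlikely related*. The order of the scale survives, because *Unlikely related* has its own criterion of no reasonable time relationship.

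**The case against.** The strongest reply is that the consequences are small. Classification rests on medical judgement, and the supporting sentences under *Related* use the language of reasonableness, which narrows the gap. In-study SAE reporting does not depend on the scale. The secondary safety endpoints in Protocol 3.2 do not use causality, and neither do the SAP's SAE tables. The Core SAP, which was not available, might already group the intermediate grades with related. The infant-death sentence sits in pregnancy text and does not cite the Section 8 scale, so it is a mismatch of wording rather than a conflicting rule. All of this bears on severity and most of it stands. It does not supply a category for the test case, and a grouping rule in the Core SAP cannot recover a judgement that the investigator was never allowed to record.

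Three stronger readings are tempting, and the documents do not support them.

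- A reader might infer that uncertain SAEs drift towards *Unrelated* and that serious suspected reactions are under-counted. *Unrelated* is equally closed on its own wording, so no direction follows.
- A reader might infer that expedited reporting is compromised. Protocol 10.1 says "This includes expedited reporting of suspected unexpected serious adverse reactions per regulatory guidelines", but it gives this duty to the sponsor and does not tie it to the Section 8 categories. The causality field on the SAE form was not available.
- A reader might give weight to the absence of a data and safety monitoring committee (Protocol 10.2). Through Follow-up Week 8 the sponsor receives every SAE regardless of causality, so this adds little.

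**Conclusion.** The point holds as a defect in a compulsory rule. Section 8 cannot be applied correctly to an SAE that has plausible timing and a credible alternative cause, and the direction in which such an event will be misclassified is uncontrolled.

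The effect is limited to three things: the causality recorded for SAEs; the related-SAE row and related-AE tables in SAP 6.4.1.2 to 6.4.1.4; and possibly the reporting of SAEs after Follow-up Week 8. The last is less certain, because Protocol 8.1.2 speaks there of belief and not of high certainty. No efficacy endpoint, secondary safety endpoint or in-study SAE reporting duty is touched.

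The number of SAEs affected cannot be given, because neither document states an SAE rate or the share of uncertain cases. The conclusion on the SAP outputs assumes that the Core SAP builds its definition of related from the investigator's Section 8 category. This should be fixed, but it does not threaten the trial's main conclusions.

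**What to change.** In Protocol Section 8, make the SAE categories exhaustive and non-overlapping. One option is to define *Related* for SAEs as a reasonable possibility that study drug caused the event, and *Unrelated* as no reasonable possibility. The other is to open *Possibly related* to SAEs and state that it counts as related.

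With either option:

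- remove the unlikely-connection wording from *Possibly related*;
- say how causality is recorded when a non-serious AE becomes serious;
- bring Protocol 8.5.1 and 9.3.2 into line with the revised scale;
- confirm in the SAP which recorded categories count as related, and check that the Core SAP agrees.

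The cost is definition wording in an amendment, updated CRF completion guidance and a note to sites. SAEs already classified under the present text would need their causality confirmed by the site before database lock. The downside is small: some SAEs may be newly labelled related. Design, sample size and dosing are unaffected.

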8.1 SERIOUS ADVERSE EVENT

8.1.1 Definition of Serious Adverse Event (SAE)

An SAE is any event that meets any of the following criteria at any dose:

- Death
- Life-threatening
- Inpatient hospitalization or prolongation of existing hospitalization
- Persistent or significant disability/incapacity
- Congenital anomaly/birth defect in the offspring of a subject who received rimegepant
- Other: Important medical events that may not result in death, be life-threatening, or require
 hospitalization, may be considered an SAE when, based upon appropriate medical judgment,
 they may jeopardize the subject and may require medical or surgical intervention to prevent
 one of the outcomes listed in this definition. Examples of such events are (but not limited to):
 - Intensive treatment in an emergency room or at home for allergic bronchospasm
 - Blood dyscrasias or convulsions that do not result in inpatient hospitalization
 - Development of drug dependency or drug abuse
 - Potential drug induced liver injury (see Section 8.4)
 - Abuse or overdose of study drug
 - Potential study drug abuse (including cases of excessive non-compliance with study drug dosing instructions or subjects who discontinue study drug without returning study drug) should be documented in the source record and reported as an AE or SAE as appropriate. Investigators must monitor subjects for possible cases of abuse of study drug (subjects taking study drug for non-therapeutic purposes, e.g. for psychoactive effects such as high or euphoria). Investigators should obtain more information and explanation from subjects when there are study drug accountability discrepancies
 - Potential study drug overdose is defined in Section 8.3

In general, hospitalization signifies that the subject has been detained (usually involving at least an overnight stay) at the hospital or emergency ward for observation and/or treatment that would not have been appropriate in the physician's office or outpatient setting. When in doubt as to whether 'hospitalization' occurred or was necessary, the AE should be considered serious.

The following hospitalizations are not considered SAEs in Pfizer clinical studies (but may be considered non-serious AEs):

- A visit to the emergency room or other hospital department <24 hours that does not result in an admission (unless considered "important medical event" or event that is life threatening).
- Elective surgery planned prior to signing consent;
- Admissions as per protocol for a planned medical/surgical procedure;
- Routine health assessment requiring admission (i.e., routine colonoscopy);
- Admission encountered for another life circumstance that carries no bearing on health and requires no medical intervention (i.e., lack of housing, care-giver respite, family circumstances).

Disability/incapacitating: An AE is incapacitating or disabling if the experience results in a substantial and/or permanent disruption of the subject's ability to carry out normal life functions.

